6.1 Safety Analysis Set

Safety analysis set defined as all subjects that are enrolled and receive at least 1 dose of AMG 910. As per the protocol, all endpoints, unless noted otherwise, will be conducted on the safety analysis set. Hence, full analysis set, primary analysis set are same as safety analysis set.

6.2 Pharmacokinetic/Pharmacodynamic Analyses Set(s)

The PK Analysis Set will contain all subjects who have received at least 1 dose of the investigational product and have at least 1 PK sample collected. A subject with insufficient number of data points to meet analysis requirements, or where significant protocol deviations have affected the data, or if key dosing or sampling information is missing will not be used to perform PK analysis.

6.3 Study Specific Analyses Set(s)

6.3.1 DLT Analyses Set(s)

Dose limiting toxicity will be performed on the DLT Analysis set. DLT Analysis **set** is defined as all subjects that are enrolled and receive at least 1 dose of AMG 910 with an evaluable DLT endpoint.

The DLT endpoint is evaluable if either: 1) the subject experiences a DLT, or 2) the subject does not experience a DLT within the DLT window in effect for the dose level cohort of the subject.

A non-evaluable subject may be replaced by an additional subject at the same dose level for dose-escalation and MTD determination.

6.3.2 RECIST Evaluable Analyses Set(s)

The analysis of objective response will be conducted on the RECIST Evaluable Analysis Set. It is defined as all subjects that are enrolled and receive at least 1 dose of AMG 910 with at least one tumor lesion that is measurable in contrast-enhanced computed tomography (CT) as defined by RECIST 1.1 **at baseline**.

Objective response will be performed through Tumor burden assessments based on RECIST 1.1 criteria.

7. Planned Analyses

7.1 Primary Analysis

Because the sponsor decided to early terminate this study, primary analysis and final analysis will be combined as one final analysis as part of study close-up activities.

7.2 Final Analysis

The final analysis will occur when target enrollment is complete for both phases and all subjects have ended the study. Data will be subject to on-going checks for integrity, completeness and accuracy in accordance with the Data Management Plan with the expectation that all outstanding data issues are resolved ahead of the snapshot. The data will be locked to prevent further changes, and a snapshot of the locked database will be used in the analysis.

8. Data Screening and Acceptance

8.1 General Principles

The objective of the data screening is to assess the quantity, quality, and statistical characteristics of the data relative to the requirements of the planned analyses.

8.2 Data Handling and Electronic Transfer of Data

The Amgen Global Study Operations-Data Management (GSO-DM) department will provide all data to be used in the planned analyses. This study will use the RAVE database.

8.3 Handling of Missing and Incomplete Data

Incomplete adverse event, **and** death dates missing data will be imputed as described in [Appendix A](#).

8.4 Detection of Bias

Lack of protocol compliance and the potential for biased statistical analyses will be examined by assessing the incidence of important protocol deviations in each cohort. The clinical study team will identify and document the criteria for important protocol deviations.

8.5 Outliers

Pharmacokinetic (PK) serum concentration data will be evaluated for outliers by visual inspection, and decisions to re-assay individual samples will be made in accordance with standard pharmacokinetic evaluation practice.

8.6 Distributional Characteristics

Where appropriate, the assumptions underlying the proposed statistical methodologies will be assessed. If required data transformations or alternative non-parametric methods of analyses will be utilized.

8.7 Validation of Statistical Analyses

Programs will be developed and maintained and output will be verified in accordance with current risk-based quality control procedures.

Tables, figures, and listings will be produced with validated standard macro programs where standard macros can produce the specified outputs.

The production environment for statistical analyses consists of Amgen-supported versions of statistical analysis software; for example, the SAS System version 9.4 or later.

9. Statistical Methods of Analysis

9.1 General Considerations

Unless otherwise specific, all described analyses will be conducted on the Safety Analysis Set. Descriptive statistics will be provided for selected demographics, safety, PK, pharmacodynamic, and biomarker data by dose, dose schedule, and time as appropriate. Descriptive statistics on continuous data will include means, medians, standard deviations, and ranges, while categorical data will be summarized using frequency counts and percentages. Graphical summaries of the data may also be presented.

Exact method proposed by Clopper-Pearson will be used for the estimation of confidence intervals (CI) for proportion.

9.2 Subject Accountability

The number and percent of subjects who were enrolled, screened but not enrolled (screen failures), enrolled but not treated, received investigational product, discontinued from AMG 910 (including reasons for discontinuing), completed study, discontinued the study (including reasons for discontinuing) will be summarized. Key study dates for the first subject enrolled, last subject enrolled, and last subject's end of study will be presented.

9.3 Important Protocol Deviations

Important Protocol Deviations (IPDs) categories are defined by the study team before the first subject's initial visit and updated during the IPD reviews throughout the study prior to database lock. These definitions of IPD categories, subcategory codes, and descriptions will be used during the study. The final IPD list is used to produce the list of Subjects with IPDs. In addition, a separate listing of all inclusion and exclusion deviations will be provided.

9.4 Demographic and Baseline Characteristics

Demographic data collection including sex, age, race, and ethnicity will be collected in order to study their possible association with subject safety and treatment effectiveness. Descriptive statistics for selected demographics, baseline characteristics, safety, PK, PD will be provided by dose, dose schedule, and time as appropriate. Descriptive statistics on

continuous data will include mean, median, standard deviation, and range, while categorical data will be summarized using frequency count and percentage. Graphical summaries of the data may also be presented.

9.5 Efficacy Analyses

9.5.1 Analyses of Primary Efficacy Endpoint(s)/Estimand(s)

No efficacy parameter is considered in primary endpoints.

9.5.2 Analyses of Secondary Efficacy Endpoint(s)

The number and percent of subjects with best overall response of complete response, partial response, stable disease, and progressive disease as determined will be tabulated. The proportion of subjects with an objective response (per RECIST 1.1) and 95% CI will be tabulated by planned dose level using the RECIST Evaluable Analysis Set.

9.5.3 Analyses of Exploratory Efficacy Endpoint(s)

Not applicable.

9.6 Safety Analyses

9.6.1 Analyses of Primary Safety Endpoints

Unless otherwise specified, statistical analyses on safety endpoints will be done using subjects from the Safety Analysis Set, which includes subjects that are enrolled and received at least 1 dose of AMG 910.

The analysis of DLTs will be conducted on the DLT Analysis Set. The probability of a subject having a DLT by planned dose level will be estimated using a two-parameter BLRM model.

9.6.2 Adverse Events

The Medical Dictionary for Regulatory Activities (MedDRA) version [25.0] or later will be used to code all events categorized as adverse events to a system organ class and a preferred term.

Subject incidence of all treatment-emergent adverse events, serious adverse events, adverse events leading to **drug interruption**, withdrawal of investigational product, fatal adverse events and subject incidence of AEs by PT will be listed, summarized and tabulated by system organ class and preferred term in decreasing frequency order.

Summaries of treatment-emergent, serious adverse events will be tabulated by system organ class, preferred term, grade (3 or higher) and dose/cohort.

In addition, separate descriptive tables will be tabulated for all treatment emergent AE, all treatment related AEs, all serious AEs, related serious AEs, treatment emergent AEs

by grade, all fatal AEs, will be tabulated and presented by cohort and dose. **Partial / missing date imputation rules are given in [Appendix A](#).**

9.6.3 Laboratory Test Results

Summaries of the absolute value and/or changes from baseline at each scheduled assessment will be provided for selected laboratory parameters. Shifts in grades of safety laboratory values from baseline for selected laboratory values will also be provided.

9.6.4 Vital Signs

[figure not shown]
Summary statistics of systolic/diastolic blood pressure, heart rate, respiratory rate, and temperature will be provided for baseline and each scheduled post-baseline assessment. Depending on the size and scope of changes, summaries of changes from baseline over time may be provided.

9.6.5 Physical Measurements

Summary of physical measurement data will be provided for weight, height, BMI.

9.6.6 Electrocardiogram

Summaries over time and/or changes from baseline over time will be provided for all ECG parameters. Subjects' maximum change from baseline in QTc will be categorized and the number and percentage of subjects in each cohort will be summarized. Subjects' maximum post baseline values will also be categorized and the number and percentage of subjects in each cohort will be summarized.

9.6.8 Exposure to Investigational Product

Investigational product exposure will be summarized for number of cycles started, number of doses, cumulative dose and average dose administered. Summaries of the of subjects with dose modifications, interruptions and reasons for modifications, interruptions will be provided. In addition, a listing of the unique manufacturing lot numbers, and a listing of the subjects administered each manufacturing lot number will be provided.

9.6.9 Exposure to Non-Investigational Product

There are no non-investigational products in this study.

9.7 Other Analyses

For AMG 910, PK parameters, including but not limited to C_{max} , minimum serum concentration (C_{min}), area under the concentration-time curve (AUC) over the dosing interval, accumulation following multiple dosing, and, if feasible, half-life ($t_{1/2}$), will be determined from the time concentration profile using standard non-compartmental approaches and considering the profile over the complete sampling interval. Based on the review of the data, analyses to describe the relationship between AMG 910 exposure and either pharmacodynamic effect and/or clinical outcome may also be performed.

9.7.1 Analyses of Pharmacokinetic or Pharmacokinetic/Pharmacodynamic Endpoints

Descriptive statistics for pharmacokinetic parameters, including but not limited to maximum serum concentration (C_{max}), minimum serum concentration (C_{min}), area under the concentration-time curve (AUC) over the dosing interval, accumulation following multiple dosing, and, if feasible, half-life ($t_{1/2}$), will be provided from the time concentration profile using standard non-compartmental approaches and considering the profile over the complete sampling interval. Individual concentration-time data will be tabulated and presented graphically.

Nominal sampling times will be used for individual concentration-time plots and tables. Actual dose administered, and actual sampling times will be used for the calculation of PK parameters for each subject. The reasons for excluding any sample from the analyses will be provided.

Summary of PK concentration over time and PK parameters will be provided. Mean concentration-time profiles for each dose will be provided. Based on the review of the data, analyses to describe the relationship between AMG 910 exposure and either pharmacodynamic effect and/or clinical outcome may also be performed. Above analyses will be conducted by Amgen Clinical Pharmacology Modeling and Simulation (CPMS).

10. Changes From Protocol-specified Analyses

There are no changes to the protocol-specified analyses.

11. References

Eisenhauer EA, P Therasse, J Bogaerts, LH Schwartz, D Sargent, R Ford, et al., 2009, New Response Evaluation Criteria in Solid Tumours: Revised RECIST guideline (version 1.1), Eur J Cancer, 45(2):228-247.

Fuchs, C. S., Doi, T., Jang, R. W., Muro, K., Satoh, T., Machado, M., Garrido, M. (2018). Safety and efficacy of pembrolizumab monotherapy in patients with previously treated advanced gastric and gastroesophageal junction cancer: phase 2 clinical KEYNOTE-059 trial. *JAMA oncology*, 4(5), e180013-e180013.

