9.4.2 Methods of Analyses

9.4.2.1 General Considerations

Unless otherwise specific, all described analyses will be conducted on the Safety Analysis Set. Descriptive statistics will be provided for selected demographics, safety, PK, pharmacodynamic, and biomarker data by dose, dose schedule, and time as appropriate. Descriptive statistics on continuous data will include means, medians, standard deviations, and ranges, while categorical data will be summarized using frequency counts and percentages. Graphical summaries of the data may also be presented.

Confidence intervals (CI) for proportions will be estimated using an exact method proposed by Clopper-Pearson (Clopper & Pearson, 1934). Kaplan-Meier methods will be used to estimate the median and percentiles for time to event endpoints with CI calculated using the Brookmeyer and Crowley method (Brookmeyer & Crowley, 1982). Kaplan-Meier methods will be used to estimate landmarks for time to event endpoints (eg, 1-year OS) with the Greenwood formula (Kalbfleisch & Prentice, 1980) used to estimate the standard error used in CI calculation.

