9.4.2.2 Efficacy Analyses

Endpoint	Statistical Analysis Methods
Primary	Not applicable
Secondary	
Listings of secondary efficacy endpoints will be produced for all subjects in the dose-escalation cohorts and the dose-expansion cohorts.
 
The proportion of subjects with an objective response (per RECIST 1.1 and per iRECIST) and 95% CI will be tabulated by planned dose level using the RECIST Evaluable Analysis Set.
 
For all subjects treated at the MTD and/or RP2D, Kaplan-Meier methods will be used to estimate the time to event curve, median time to event and percentiles with 95% CI for 1) duration of response (RECIST 1.1 and iRECIST) 2) time to progression 3) PFS 4) OS. For all subjects treated at the MTD and/or RP2D, Kaplan-Meier methods will be used to estimate 6-month and 1-year PFS, 1-year and 2-year OS with 95% CI.

Exploratory	Will be described in the statistical analysis plan finalized before database lock.
--------------------	------------------------------------------------------------------------------------

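### SAP Section 10 declares no change, yet six protocol-planned outputs (iRECIST response, efficacy listings, Kaplan-Meier analyses, DLT tabulations) are absent from the SAP

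*SAP*

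**What the plan says.** **Protocol.** Section 9.4.2.2 requires efficacy listings: "Listings of secondary efficacy endpoints will be produced for all subjects in the dose-escalation cohorts and the dose-expansion cohorts". It plans response by two sets of criteria: "The proportion of subjects with an objective response (per RECIST 1.1 and per iRECIST) and 95% CI will be tabulated by planned dose level". For subjects at the MTD and/or RP2D it plans Kaplan-Meier curves, medians and percentiles for DOR, TTP, PFS and OS, and landmark estimates: "For all subjects treated at the MTD and/or RP2D, Kaplan-Meier methods will be used to estimate 6-month and 1-year PFS", together with 1- and 2-year OS. Section 9.4.2.1 gives the general method, "Kaplan-Meier methods will be used to estimate the median and percentiles for time to event endpoints", with Brookmeyer-Crowley intervals and Greenwood standard errors. Section 9.4.2.3.1 plans three things for DLT: subject incidence by planned dose level, a DLT table, and the two-parameter BLRM estimate.

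**SAP.** Section 2.1 lists the same secondary efficacy endpoints as the protocol: objective response by RECIST 1.1 and iRECIST, DOR, TTP, PFS with landmarks, and OS with landmarks. Section 9.5.2, the whole of the secondary efficacy analysis, contains a best overall response table and this: "The proportion of subjects with an objective response (per RECIST 1.1) and 95% CI will be tabulated by planned dose level". Section 6.3.2 confirms the restriction: "Objective response will be performed through Tumor burden assessments based on RECIST 1.1 criteria". Section 9.1 keeps the protocol's rule for proportions, "Exact method proposed by Clopper-Pearson will be used for the estimation of confidence intervals (CI) for proportion", and has no Kaplan-Meier text. Section 9.6.1 keeps only the BLRM estimate for DLT. Section 7.1 reports early termination and merges the primary and final analyses. Section 10 then states "There are no changes to the protocol-specified analyses".

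**The concern.** Section 10 is where a reader looks to learn which analyses differ from the protocol and why. Someone relying on it would expect iRECIST response, the efficacy listings, the time-to-event analyses and the DLT tables in the report. Someone programming from Section 9 would produce none of them.

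Two consequences follow. DOR, TTP, PFS, OS and iRECIST response would either be left out of the report or be settled outside the plan, after the data are known. DLT, a primary endpoint, would be reported only through a model that borrows across doses, with no specified display of how many evaluable subjects had a DLT at each dose.

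**Working it through.** The check is a comparison of texts, followed by a count and one illustration.

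**1. Planned outputs against the SAP**

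| Protocol output | Protocol section | In the SAP? | Conditional on MTD/RP2D? |
|---|---|---|---|
| 1. iRECIST objective response, 95% CI, by planned dose level | 9.4.2.2 | No; 9.5.2 and 6.3.2 name RECIST 1.1 only | No |
| 2. Listings of secondary efficacy endpoints, all subjects | 9.4.2.2 | No; none in 9.5 | No |
| 3. Kaplan-Meier curve, median, percentiles for DOR, TTP, PFS, OS | 9.4.2.1, 9.4.2.2 | No; absent from 9.1 and 9.5.2 | Yes |
| 4. Kaplan-Meier 6-month and 1-year PFS, 1- and 2-year OS | 9.4.2.1, 9.4.2.2 | No | Yes |
| 5. DLT incidence by planned dose level | 9.4.2.3.1 | No; 9.6.1 has the BLRM only | No |
| 6. DLT table | 9.4.2.3.1 | No | No |

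Six outputs are missing: 4 unconditional and 2 conditional. Redaction does not explain this, because SAP 9.1, 9.5.1 to 9.5.3 and 9.6.1 read as complete.

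**2. Endpoints against analyses.** SAP 2.1 has 4 primary bullets, 1 PK bullet and 5 secondary efficacy bullets, so 4 + 1 + 5 = 10.

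- No specified analysis: DOR, TTP, PFS, OS = 4.
- Half covered: objective response (RECIST 1.1 but not iRECIST) = 1.
- Covered at least in part by a named method: 4 primary + 1 PK = 5.

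Within secondary efficacy, 4 of 5 have none and 1 of 5 is half covered.

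**3. Could the missing analyses be run from the documents anyway?** Protocol 9.4.2.1 names the Kaplan-Meier method. Neither document gives the start date, event and censoring rules for DOR, TTP, PFS or OS, and SAP Section 5 defines none of them. Protocol 9.3.4 refers missing-data handling to the SAP, which supplies only date imputation (8.3 and Appendix A). Appendix A still censors survival time when a death date is missing or in error, and the reference list still cites Brookmeyer-Crowley and iRECIST. No SAP analysis uses these remnants.

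**4. Why the BLRM estimate cannot replace the DLT count.** Inputs from Protocol Appendix 9: ln(a) ~ N(-0.847, SD 1.275), ln(b) ~ N(-1.098, SD 1.981), correlation 0, reference dose 3500 µg. Model form assumed: logit p(dose) = ln(a) + b × ln(dose/3500). Data assumed for illustration only: 3 evaluable subjects at each of 6.5, 15 and 30 µg, with 1 DLT among the 9. Posterior means come from numerical integration over a grid.

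| Dose at which the one DLT occurred | BLRM mean DLT probability at 30 µg | Observed incidence at 30 µg |
|---|---|---|
| 6.5 µg | 14.3% | 0/3 = 0% |
| 15 µg | 13.8% | 0/3 = 0% |
| 30 µg | 13.3% | 1/3 = 33% |

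The model estimate moves by 1 percentage point (14.3 − 13.3) while the observed incidence moves by 33. In this example it even falls slightly when the event is at 30 µg, because a DLT at a lower dose raises the whole curve. A reader cannot recover the counts by dose from the estimate.

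**The case against.** The strongest reply is that the SAP describes itself as adding detail to the protocol, so declaring no change may mean that the protocol's analyses remain in force. On that reading the defect is missing detail and nothing has been dropped. The leftover survival-censoring rule and references fit that reading, though they fit incomplete trimming equally well. Even so, the analyses could not be run consistently without definitions, and SAP 9.5.2 restates the protocol's response analysis with iRECIST taken out, which is an alteration.

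Several narrower points carry weight.

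- **Kaplan-Meier.** These outputs were limited to the MTD/RP2D. If no such dose was declared before termination, only the listings of DOR, TTP, PFS and OS were owed.
- **iRECIST.** Protocol Appendix 12 says evaluations under the two criteria coincide until RECIST 1.1 progression, so the lost table may differ for few subjects.
- **DLT.** SAP 9.1 promises counts and percentages for selected safety data by dose, and SAP 6.3.1 keeps a DLT Analysis Set. DLT is not named in 9.1, so this softens the gap without closing it. Items 5 and 6 are adjacent sentences and could be counted as one. The illustration uses invented outcomes and measures no effect in this trial.
- **Early termination.** A shorter analysis may well be reasonable in a descriptive phase 1 study. That is a reason to record in Section 10; neither Section 7.1 nor Section 10 records it.

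The six items are also not a full inventory. Covariates and biomarker subgroups (Protocol 9.3.2 and 9.3.3) and exploratory efficacy (Protocol 9.4.2.2) are marked not applicable in SAP 4.1, 4.2 and 9.5.3. The QTcF categories of Protocol 9.4.2.3.6 became QTc in SAP 9.6.6. This strengthens the case against the statement in Section 10.

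**Conclusion.** The concern holds. The no-change statement is inaccurate, and following the SAP as written would omit four unconditional protocol outputs, two of them for a primary endpoint. The two Kaplan-Meier outputs are also missing; whether they were owed depends on whether an MTD or RP2D was declared, which the documents do not state.

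This should be fixed, but it does not invalidate the study: every primary endpoint keeps some analysis, no efficacy endpoint is primary, and data from an early-terminated study may be sparse. The conclusion rests on the visible text alone and on no assumption about the results. The BLRM figures depend on the assumed counts and model form and serve only to show the difference between a model estimate and an observed count.

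A related side point, on which the conclusion does not depend: SAP 7.2 repeats the protocol's trigger of complete enrollment in both phases, which conflicts with the early termination reported in SAP 7.1.

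**What to change.** - **SAP 9.5.2.** Restore iRECIST objective response with exact 95% CI by planned dose level, and the all-subject listings of DOR, TTP, PFS and OS. Add start date, event and censoring rules for each to Section 5. State whether an iRECIST response needs confirmation: Protocol Appendix 12 says the immune best overall response does not, while Protocol 8.2.2 asks for confirmation of partial and complete responses.
- **SAP 9.6.1.** Restore DLT incidence by planned dose level and the DLT table beside the BLRM estimate.
- **Kaplan-Meier.** Keep the protocol's analyses, with their interval methods, if an MTD or RP2D was declared. Otherwise record in Section 10 that they are not done and why.
- **SAP 7.2.** Replace the enrollment trigger with the database lock that follows early termination.
- **SAP 10.** Replace the no-change sentence with a list of every omitted or altered analysis and its reason, including the covariate, subgroup, exploratory and QTc differences. If the sponsor prefers not to restore an output, an entry here is the minimum that removes the contradiction.

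The cost is SAP wording and modest programming of standard tables and listings, with no new data collection. With few subjects, the restored listings will be descriptive only.
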